## 2. Background Information

Emergency contraception (EC) is used to prevent unwanted pregnancy after unprotected sexual intercourse (UPSI) or after a recognised contraceptive failure such as condom accidents or missing doses of hormonal contraception. Availability of effective EC methods is very important for reducing the occurrence of unwanted pregnancies in these circumstances.

Oral hormonal EC is the most widely adopted EC method in both Hong Kong and most other countries. The EC method currently available for oral use consists of a single dose of 1.5 mg levonorgestrel (LNG) to be taken within 72 hours of UPSI, or 30 mg ulipristal acetate (UPA) to be taken within 120 hours of UPSI (Glasier et al, 2014; Faculty of Sexual and Reproductive Health, 2017).

Studies have shown that LNG is effective as an EC only when given before, but not after, ovulation (Novikova et al, 2007; Noe et al, 2010). This may be explained by its mechanism of action. LNG prevents pregnancy by blocking or postponing the luteinizing hormone (LH) surge, hence disrupting the ovulatory process; this effect is limited to its administration before the onset of the LH surge, but not when it is taken after the LH surge has commenced, a time when intercourse is most likely to result in pregnancy. The more advanced in the follicular phase that LNG is taken, the lower will be its ability to block ovulation and thus prevent fertilization after UPSI (Croxatto et al, 2004). Once the ovulatory process has been triggered by the LH surge, LNG cannot prevent the follicle from rupturing and releasing the oocyte. It was also shown that LNG has no effect on sperm function, fertilization and implantation (Cameron et al, 2017).

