### 5. Subject selection and exclusion

#### 5.1 Inclusion criteria

Women attending the Family Planning Association of Hong Kong for oral EC will be recruited if they fulfil the following criteria:

- (a) healthy women aged 18 years or above;
- (b) requesting emergency contraception within 72 h of a single act of unprotected intercourse in the current menstrual cycle;
- (c) having menstrual cycles between 24 and 42 days
- (d) willing to abstain from further acts of unprotected intercourse and;
- (e) available for follow-up over the next 6 weeks.

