## 6. Treatment of subjects

### 6.1 Baseline assessment:

- The subject will be assessed and counselled for the use of EC by the clinic nurse or doctor as routine. Suitable subjects will be enrolled for the study after informed consent.
- A menstrual history will be taken.
- Pregnancy test will be done; only those tested negative will be recruited into study.
- Blood (5 ml into clotted bottle) will be collected for hormonal assay (LH, oestradiol, progesterone). The serum hormonal levels will be used to estimate the cycle day at the time of presentation in relation to the day of ovulation based on the method described by Novikova et al (2007).

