### Secondary outcome measures:

- Pregnancy rate (%)
- Change in length (shortening / lengthening) of current cycle (days)
- Adverse effects

The data collection sheet is included in Appendix 1. All the clinical data are part of the usual consultations for EC provision.

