## 9. Statistics

### 9.1 Statistical tests:

- The efficacy-evaluable population will include all women who are enrolled into the study and can be contacted for a follow-up where the outcome data are collected.
- Cases with missing data in a certain parameter will not be analysed for that specific parameter; no data imputation will be instituted.
- The percentage of pregnancies prevented will be compared between groups by  $\chi^2$  test.
- Logistic regression model using Firth's bias reduction method will be applied to compare the pregnancy rates between groups. Confidence intervals for regression coefficients will be computed by penalised profile likelihood. This is a statistical method recommended for rare events (Puhr R, Heinze G, Nold M, Lusa L, Geroldinger A. Firth's logistic regression with rare events: accurate effect estimates and predictions? Stat Med 2017; 36(14): 2302-2317).
- The rate of occurrence of menstrual changes will be compared between groups using  $\chi^2$  test (for nominal categorical variables) and  $\chi^2$  test for trend (for ordinal categorical variables).

- The rate of occurrence of adverse events will be compared between groups by Fisher's exact test as some of the cells may contain an expected frequency of less than 5.
- Continuous variables between the two groups will be compared by Student's t-test.
- Statistical analyses will be performed using SPSS version 28 (IBM Corporation, New York, USA), MedCalc version 20 (MedCalc Software Limited, Ostend, Belgium) and R package "logistf" Version 4.1.2 (<http://www.r-project.org>).
- P-value <0.05 will be considered as statistically significant.

Two subgroup analyses will be performed. The first subgroup analysis will stratify participants into pre-ovulatory versus post-ovulatory at the time of EC based on blood results of serum oestradiol, progesterone and luteinising hormone level on the day of EC (Li et al, 2016). The second subgroup analysis will stratify participants within versus over the body weight limits recommended for the usual dose of LNG-EC (by the cut-off of body mass index at 26 kg/m^2 and that of body weight at 70 kg).

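### The cycle-length secondary outcome is planned for an unadjusted t-test, which is valid but leaves two baseline predictors unused; a prespecified linear model is a cheap gain in precision

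*Combined protocol and SAP*

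**What the plan says.** Section 7 lists as a secondary outcome "Change in length (shortening / lengthening) of current cycle (days". The unit makes this a continuous variable. The reference length is not stated, though shortening or lengthening implies the woman's usual cycle.

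Two lines in section 9.1 could apply. The general one is "Continuous variables between the two groups will be compared by Student's t-test". The other is "The rate of occurrence of menstrual changes will be compared between groups using" chi-square tests, and it is limited to nominal or ordinal categories. Section 9.1 names no baseline covariate for any analysis.

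Baseline data that bear on this outcome:

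- Section 5.1 requires "having menstrual cycles between 24 and 42 days", and section 6.1 says "A menstrual history will be taken".
- Section 6.1 also says "The serum hormonal levels will be used to estimate the cycle day at the time of presentation in relation to the day of ovulation".
- Section 9.1 uses ovulatory status in one way: "The first subgroup analysis will stratify participants into pre-ovulatory versus post-ovulatory at the time of EC".

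Section 4 describes 1:1 blocked allocation and names no stratification factor.

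**The concern.** A change score subtracts usual length with a fixed coefficient of 1. That is fully efficient only if current length rises by one day for each extra day of usual length. Entry allows an 18-day spread of usual lengths (42 − 24). With imperfect correlation, women reporting long cycles will tend to shorten and women reporting short cycles to lengthen, whatever they receive. That regression to the mean adds noise to the comparison.

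Ovulatory status at dosing is a second plausible predictor. Section 2 says "LNG prevents pregnancy by blocking or postponing the luteinizing hormone (LH) surge, hence disrupting the ovulatory process", and both arms receive LNG, so cycle timing may differ between women dosed before and after ovulation. The planned subgroup split does not adjust the overall comparison for this.

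What is at stake is the width of the confidence interval for one secondary outcome. The primary outcome is not touched.

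**Working it through.** **The plan's own figure.** Section 9.2 gives no SD, power or sample size for cycle length, only a sample size for the primary outcome. With 52% versus 62%, two-sided 0.05 and 80% power:

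n = [1.960·√(2 × 0.57 × 0.43) + 0.8416·√(0.52 × 0.48 + 0.62 × 0.38)]² / 0.10² = 383.6, so 384 per group, as stated.

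384 / 0.9 gives 427 per group, or 854 in total, against 860 planned. Evaluable women per arm: 860 × 0.9 / 2 = 387, used below.

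**Inputs that must be assumed.** SD of usual length sB = 3 or 4 days; SD of current length sF = 5 days; correlation r = 0.3 or 0.5.

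**Formulae.**
- Change score: V1 = sB² + sF² − 2·r·sB·sF
- Linear model with usual length as covariate: V2 = sF²(1 − r²)
- V1 − V2 = (sB − r·sF)², which is never negative
- Equivalent extra women per arm: 387 × (V1/V2 − 1)
- 95% CI half-width: 1.96·√(2V/387)

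| sB | r | V1 | V2 | Reduction | Extra women per arm | Half-width, t-test → adjusted (days) |
|---|---|---|---|---|---|---|
| 4 | 0.3 | 29.0 | 22.75 | 21.6% | 106 | 0.76 → 0.67 |
| 4 | 0.5 | 21.0 | 18.75 | 10.7% | 46 | 0.65 → 0.61 |
| 3 | 0.3 | 25.0 | 22.75 | 9.0% | 38 | 0.70 → 0.67 |
| 3 | 0.5 | 19.0 | 18.75 | 1.3% | 5 | 0.614 → 0.610 |

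**Sensitivity.** Widening to sF = 4 to 6 and r = 0.2 to 0.6 gives 0 to 40%. The ends are sB = 3, sF = 5, r = 0.6, where (3 − 3)² = 0, and sB = sF = 4, r = 0.2, where V1 = 25.6 and V2 = 15.36.

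**Ovulatory status.** Suppose half the women are dosed before ovulation, mean change differs by D = 2 to 3 days between the two states, status is unrelated to usual length, and this spread is already inside the SD of 5. The term then removes D²/4 = 1.0 to 2.25 days². The total reduction against the t-test becomes 1 − (18.75 − 1.0)/19.0 = 6.6% at the low end and 1 − (22.75 − 2.25)/29.0 = 29% at the high end. D is purely an assumption.

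**Chance imbalance.** The slope is r·sF/sB, here 0.375 to 0.83. An imbalance d in mean usual length moves the unadjusted difference by (1 − slope)·d in size. For d = 0.5 day this is 0.08 to 0.31 day. The SE of d is sB·√(2/387) = 0.22 to 0.29 day, so 0.5 day is 1.7 to 2.3 SEs, with a two-sided probability of about 2 to 8%. The variance of this shift is (sB − r·sF)² × 2/387, exactly the excess in V1. Imbalance and lost precision are therefore one cost, not two.

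**The case against.** The strongest reply is that nothing here is wrong, only improvable. A reader might infer that chance imbalance in usual length makes the t-test biased, or turns noise into a false treatment effect. The documents do not support that. Allocation is randomised, so the t-test is unbiased on average, keeps its type I error, and already carries chance imbalance in its standard error. This part of the objection stands.

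Four further points also stand in part:

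- **Reference and test.** Usual length as the reference is inferred, and whether it is recorded as a single number depends on the data collection sheet in Appendix 1, which is not in the text reviewed. The chi-square line could be read as covering this outcome. The unit of days favours the t-test, but the plan should settle it.
- **Ovulatory status is not ignored.** It defines a planned subgroup analysis, which could show an effect confined to one state better than an additive covariate would. That does not sharpen the overall comparison.
- **Section 2 says nothing about cycle length.** It describes LNG's action on the LH surge and ovulation. That ovulatory status predicts cycle length is plausible but not stated. Nor does the plan call this outcome a test of mechanism.
- **Missing hormone results.** Section 9.1 excludes cases with missing data and allows no imputation. A model requiring hormone status could drop women and lose some of the gain. The fix must deal with this.

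None of this removes the core point: covariates likely to be in hand are not used where they would help.

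**Conclusion.** The concern holds as one of efficiency, not validity. As written, section 9.1 would give a valid but possibly wider interval than the baseline data allow. The reduction in residual variance from adjusting for usual length is about 1 to 22% under the main assumptions and 0 to 40% over the wider grid. It is near zero if the slope on usual length is close to 1. Any further gain from ovulatory status is also assumed. Since the documents give no SDs or correlation, they cannot show that the loss is material.

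The case for acting is the asymmetry: apart from the degrees of freedom used, adjustment does not raise the residual variance, and it needs no new data if usual length is recorded. The effect is confined to one secondary outcome with no stated power. The primary analysis and the planned 384 per group and 860 in total are unaffected.

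**What to change.** In section 7, state the reference for the change, for example the usual cycle length reported in the baseline menstrual history, and confirm that the data collection sheet records it as a number of days.

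In section 9.1:

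- For cycle length in days, replace the t-test as the main analysis with a linear model. The response is current cycle length; the terms are treatment, usual cycle length (continuous) and ovulatory status at dosing, classified as for the planned subgroup. Using the change as response gives the same treatment estimate once usual length is in the model.
- Give ovulatory status an 'unknown' category, so that no woman is dropped for a missing hormone result. This imputes nothing and so fits the existing missing-data rule.
- Report the adjusted mean difference with its 95% CI, and keep the unadjusted t-test as supportive.
- State that the chi-square line covers only menstrual changes recorded as categories.

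The cost is a few sentences and slightly more analysis work. With usual length recorded, no extra data, visits or participants are needed, and SPSS, already named in the plan, fits the model. The three added terms (usual length and two for a three-level status) use 3 of the 772 residual degrees of freedom that the t-test has with 774 evaluable women (2 × 387). The change should be made before the treatment codes are revealed.

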UPA, another selective progesterone receptor modulator, has more recently been introduced as an oral EC. Two randomized controlled trials showed that UPA was as effective as LNG for EC within 72 hours of UPSI (Creinin et al, 2006; Glasier et al, 2010). When the results of the two RCTs were combined in a meta-analysis, UPA has significantly lower failure rate compared to LNG [1.36% (22/1617) vs 2.15% (35/1625),  $p=0.046$ ] (Glasier et al, 2010). The effectiveness of UPA as EC is maintained up to 120 hours after UPSI, which is currently the licensed indication of UPA. In contrast to LNG which has a limited administration period preceding the onset of the LH surge for it to be effective, it was demonstrated that a single dose of 30 mg UPA administered up till the time immediately before the LH peak could still significantly interfere with follicular rupture (Brache et al, 2010). It was initially postulated in some studies that UPA might also have some concurrent inhibitory effect on embryo implantation based on changes in some molecular and histological parameters induced by UPA, but this was not supported by subsequent in-vitro co-culture experiments. One study in Hong Kong also did not support a significant clinical effect of UPA as EC when administered post-ovulation (Li et al, 2016). Therefore, the journey in search of further improvement in the efficacy of oral EC methods, particularly one with effective post-ovulatory action, still continues.

Prostaglandins are “local hormones” that take part in a number of reproductive processes including ovulation (Duffy, 2015), fertilisation (Sugimoto et al, 2015), tubal function (Wanggren et al, 2006; Wanggren et al, 2008) and embryo implantation (Salleh, 2014). Hence, it is postulated that an inhibitor of the cyclo-oxygenase (COX) enzyme, the key enzyme involved in prostaglandin production, may potentially confer a “contraceptive”

effect and may act synergistically with LNG for EC, particularly to target at the post-ovulatory events in addition.

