Existing clinical trials which explored the effect of several COX-2 inhibitors on ovulatory function were reviewed in a recent publication (Weiss and Gandhi, 2016); this included six clinical trials exploring the effect of rofecoxib, meloxicam and celecoxib on human ovulatory function. It was suggested that administration of these COX-2 inhibitors in the follicular phase could disrupt or delay follicle rupture, but in most of these studies the drug was administered consecutively for at least 5 days, which would be inconvenient in the context of emergency contraception and compliance may be an issue. Only one study explored the use of a single dose of meloxicam concurrently with LNG 1.5 mg; a trend of increased incidence of unruptured follicles was reported in the LNG plus meloxicam group compared to the LNG plus placebo group, and yet statistical significance was not reached, probably due to the small sample size (n=41). There were little data on the clinical effect of COX inhibitors on post-ovulatory events such as embryo implantation.

Based on the above information, we hypothesize that inhibition of prostaglandin synthesis by a COX inhibitor may confer additional contraceptive action when administered in adjunct to the current LNG regimen, as this may result in disruption of both ovulatory and post-ovulatory events involved in the establishment of conception. Blocking prostaglandin synthesis may retard tubal activities and hence slow down embryo transport, leading to delayed arrival of the embryo to the uterine cavity beyond the implantation window. Furthermore, any negative effect of reduced prostaglandin synthesis on endometrial receptivity may further potentiate its contraceptive action. Hence, it is hoped that COX inhibitor and LNG may act synergistically to achieve an enhanced efficacy for EC.

We choose to investigate the effect of piroxicam, one of the longest-acting COX inhibitor (with half-life over 50 hours) that is commercially available, at a single oral dose of 40 mg. An oral dose of piroxicam up to 40 mg is used pharmacologically for pain relief. Although small clinical studies in women undergoing assisted reproduction treatment showed that a low dosage (10 mg) of piroxicam did not interfere with, or might even enhance, implantation rate (Moon et al, 2004; Firouzabadi et al, 2007; Dal Prato and Borini, 2009; Kumbasar et al, 2017), it is probable that a higher dose may prevent implantation.

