### 3. Objectives:

Aim: To compare the percentage of pregnancies prevented by LNG co-administered with piroxicam or placebo for oral emergency contraception by a randomised controlled trial.

Hypothesis to be tested: LNG plus piroxicam has higher percentage of pregnancies prevented compared with LNG plus placebo for oral emergency contraception.

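### The two subgroup analyses are planned by stratification only, with no treatment-by-subgroup interaction to test whether the piroxicam effect differs

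*Combined protocol and SAP*

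**What the plan says.** Section 9.1 of the combined protocol and SAP announces two subgroup analyses and describes each by how the women are divided:

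- Ovulatory status: "The first subgroup analysis will stratify participants into pre-ovulatory versus post-ovulatory at the time of EC based on blood results".
- Weight: "The second subgroup analysis will stratify participants within versus over the body weight limits recommended for the usual dose of LNG-EC", with cut-offs of BMI 26 kg/m² and 70 kg.

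The efficacy methods in the same section compare the arms. A χ² test is used for the fraction of pregnancies prevented. For the secondary pregnancy rate, "Logistic regression model using Firth's bias reduction method will be applied to compare the pregnancy rates between groups". One rule covers everything: "P-value <0.05 will be considered as statistically significant".

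No section names an interaction or heterogeneity test, a model with a subgroup term, an endpoint for the subgroups, or an exploratory label. The only stated hypothesis, in section 3, is overall: "LNG plus piroxicam has higher percentage of pregnancies prevented compared with LNG plus placebo for oral emergency contraception". Section 2 gives the mechanistic reason for adding a COX inhibitor, "particularly to target at the post-ovulatory events in addition".

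**The concern.** A p-value below 0.05 in one stratum and above it in the other does not test whether the effects differ. The two p-values can fall on opposite sides of 0.05 because of chance, or because the strata hold different numbers of events, while the true effects are identical. The test for a difference is the treatment-by-subgroup interaction, and the plan does not include one.

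This matters most for ovulatory status. Section 2 says that LNG works before but not after ovulation and looks for a method with post-ovulatory action. A lone significant post-ovulatory stratum would naturally be read as evidence of that action. The weight split invites the same reading about women above the limits for usual-dose LNG. What is at stake is a secondary claim of a differential effect.

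**Working it through.** **The plan's own figure.** Section 9.2 uses 52% versus 62%, 80% power and type I error 0.05. Two-sided with pooled variance:

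n = [1.960·√(2·0.57·0.43) + 0.842·√(0.52·0.48 + 0.62·0.38)]² / 0.10² = (1.372 + 0.586)² / 0.01 ≈ 384 per arm, as stated. Allowing for 10% default, 384/0.9 = 427 per arm, or 854 in total; the plan recruits 860. This covers the overall comparison only. No figure is given for the subgroups.

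**Expected pregnancies.** Assumption: the pooled LNG failure rate cited in section 2 (35/1625 = 2.154%) applies to the placebo arm.

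- Piroxicam arm: 2.154% × (1 − 0.62)/(1 − 0.52) = 2.154% × 0.38/0.48 = 1.705%.
- Per 384 women: 8.27 and 6.55, so about 14.8 pregnancies in 768 women.
- Equal strata (192 per arm in each): about 4.1 versus 3.3 in each stratum.
- 80/20 split (307 and 77 per arm): 6.6 versus 5.2 in the larger stratum, 1.7 versus 1.3 in the smaller.

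The documents give no stratum sizes, so both splits are assumptions. The control rate is also assumed equal in the two strata.

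**How often exactly one stratum is significant.** Within each stratum, take the Firth penalised likelihood-ratio test at two-sided 0.05. In a saturated model this amounts to adding 0.5 to every cell. Enumerate all binomial outcomes to obtain rejection probabilities s1 and s2. Then P(exactly one) = s1(1 − s2) + s2(1 − s1) and P(both) = s1·s2.

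| Scenario | s1, s2 | Exactly one | Both | Neither | Interaction p<0.05, given exactly one |
|---|---|---|---|---|---|
| 50/50, same effect | 4.3%, 4.3% | 8.3% | 0.2% | 91.6% | 30% |
| 50/50, no effect | 3.6%, 3.6% | 7.0% | 0.1% | 92.9% | 36% |
| 80/20, same effect | 5.8%, 0.9% | 6.6% | 0.05% | 93.4% | 18% |
| 80/20, no effect | 4.3%, 1.1% | 5.2% | 0.04% | 94.7% | 23% |

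**Misleading results that the interaction would catch (same effect in both strata).**

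- 50/50: 8.26% × (1 − 0.299) = 5.8% of all trials.
- 80/20: 6.59% × (1 − 0.177) = 5.4% of all trials.

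**Precision of the interaction at rounded expected counts.** These are ratios of odds ratios with penalised-profile 95% CIs.

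- 4/192 versus 3/192 in both strata: 1.0 (0.13 to 7.7).
- 7/307 versus 5/307, and 2/77 versus 1/77: 0.81 (0.06 to 8.3).

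**Interaction power if piroxicam works in one stratum only.**

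| Share of women in that stratum | Pregnancies halved there | 80% reduction there |
|---|---|---|
| 50% | 7.9% | 16.4% |
| 30% | 5.1% | 8.3% |
| 20% | 3.0% | 4.2% |

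**The case against.** **The plan never says that it will compare stratum p-values.** A reader might infer that the sponsor intends to claim a differential effect from them. The documents do not support that. Section 3 states overall superiority only, and section 2 expects action at both stages: "this may result in disruption of both ovulatory and post-ovulatory events involved in the establishment of conception". This is an omission in a short plan, not a contradiction. The point stands only in that form: the listed tests cannot answer the question that the subgroups raise.

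**The conditional figure overstates the problem.** With equal strata, 98% of trials with any significant stratum have just one. That follows almost automatically from two independent tests that each reject about 4% of the time. It should not lead, because about 92% of trials show no significant stratum at all. This objection is accepted.

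**The size depends on assumptions.** Equal control rates across ovulatory strata are doubtful, since section 2 says LNG works only before ovulation. With equal strata and control rates from 1.5%/2.8% to 0.5%/3.8%, exactly one stratum is significant in 7.7% to 6.1% of trials, so the picture barely changes. If 52% and 62% are instead treated as per-woman proportions, as section 9.2 does, the figure is 50-61%. The event-based figure is closer to what the trial can observe and is the one used here.

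**The gain is small.** With about 15 pregnancies, counts by arm and stratum under an exploratory label would give much of the protection. In 18-30% of the one-stratum trials the interaction is also significant although the true effects are equal, so it does not correct those. Both statements are true. Low power supports the exploratory label. It is no reason to leave out the one estimate that addresses the question and shows how uncertain the answer is.

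**Conclusion.** The concern holds as a low-cost improvement to secondary analyses. As written, the plan yields within-stratum p-values and nothing that compares them.

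If the true effect is the same in both strata, 6.6-8.3% of trials would show exactly one significant stratum. In about 70-82% of those, 5-6% of all trials, the interaction would not support a difference. These figures rest on the 2.15% control rate holding in both strata, the 52% versus 62% design, 384 evaluable women per arm and splits from 50/50 to 80/20. The rate and the splits are assumptions.

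A reader might also infer that the primary result or the sample size is compromised. Neither is: both concern the overall comparison, which the subgroup analyses leave unchanged. The unnamed subgroup endpoint is missing detail, not an error in itself.

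**What to change.** For each subgroup factor, fit a Firth logistic model for pregnancy (yes/no) with treatment, subgroup and treatment-by-subgroup terms. Report the interaction estimate with its penalised-profile CI, beside pregnancy counts per arm and stratum. Base any claim of a differential effect on that interaction, and label both analyses exploratory.

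Two details need settling in section 9.1:

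- State that the subgroup endpoint is the secondary pregnancy rate. The model does not contain expected pregnancies, so it does not address the primary fraction prevented.
- Either give one rule that combines the BMI and weight cut-offs, or fit one model for each.

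The cost is SAP wording and two extra terms (a subgroup main effect and the product) in each model. The software and interval method are already planned, and no extra participants are needed. The drawback is imprecision: power is about 3-16% for the effects considered. The interaction guards against a false claim of a difference but will rarely detect a true one, so subgroup conclusions will be weaker.
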